### 10.2. Populations for Analyses

#### 10.2.1. Study Participant Disposition

A detailed description of subject disposition will be provided at the end of the study.

#### 10.2.2. Study Participant Characteristics

The subject's age, sex, weight, BMI, height, race/subrace, and other demographic data will be summarized by dosing regimen and overall.

### 10.3. Statistical Analyses

Statistical analysis of this study will be the responsibility of Eli Lilly and Company or its designee.

Pharmacokinetic analyses will be conducted on the full analysis set. This set includes all data from all randomized subjects receiving the dose of LY3074828 with evaluable PK data. Safety analyses will be conducted for all subjects receiving a dose of LY3074828, whether or not they completed all protocol requirements.

Additional exploratory analyses of the data will be conducted as deemed appropriate. Study results may be pooled with the results of other studies for population PK analysis purposes to avoid issues with post-hoc analyses and incomplete disclosures of analyses.

No adjustments for multiple comparisons will be made.

### **10.3.1. Safety Analyses**

#### **10.3.1.1. Clinical Evaluation of Safety**

All IP and protocol procedure AEs and PCs will be listed, and if the frequency of events allows, safety data will be summarized using descriptive methodology.

The incidence of symptoms for each treatment will be presented by severity and by association with IP as perceived by the investigator. Symptoms reported to occur prior to study entry will be distinguished from those reported as new or increased in severity during the study. Each symptom will be classified by the most suitable term from the medical regulatory dictionary.

The number of IP- and device-related SAEs and any related PCs will be reported.

#### **10.3.1.2. Statistical Evaluation of Safety**

##### **10.3.1.2.1. *Injection-site Pain***

The intensity of pain at the injection site within 1 minute of the end of injection and 5 minutes after the end of the injection will be evaluated, as reported by the subject and measured according to the 0- to 100-mm VAS. Assessments will also be performed at 15 minutes post-injection; however, the primary endpoints will be the 1- and 5-minute assessments. For 1-mL PFS, the second injection will be administered 20 ( $\pm 2$ ) minutes after the first injection.

Descriptive statistics will be used to summarize the intensity of pain at each time point.

A linear fixed-effects model will be used to analyze the post-injection pain VAS scores. The model will include device and injection location as fixed effects. The least squares (LS) means and differences in LS means will be presented along with the corresponding 90% CI. The distribution of the data will be explored prior to analysis to determine whether data transformation is required. It is possible that the pain scores will be 0, so if the distribution of the data implies that a log-transformation is required then the score may be updated to  $\log(\text{VAS}+1)$  to allow for the inclusion of the 0 values in the analysis.

##### **10.3.1.2.2. *Duration of Injection***

The duration of the injection (measured in seconds) will be summarized for each drug delivery device for each injection site.

##### **10.3.1.2.3. *Injection-site Assessments***

The incidence of the following AEs will be listed and summarized for each drug delivery device for each injection site: erythema, induration, pruritus, and edema. Occurrence of bleeding will be listed.

#### **10.3.1.2.4. Statistical Evaluation of Other Safety Parameters**

Other safety parameters that will be assessed include clinical laboratory parameters and vital signs. The parameters and changes from baseline (predose), where appropriate, will be listed and summarized using standard descriptive statistics. Additional analyses will be performed if warranted upon review of the data.

### **10.3.2. Pharmacokinetic Analyses**

#### **10.3.2.1. Pharmacokinetic Parameter Estimation**

Pharmacokinetic parameter estimates for LY3074828 will be calculated by standard noncompartmental methods of analysis.

The primary parameters for analysis will be  $AUC(0-\infty)$ ,  $AUC(0-t_{last})$ , and  $C_{max}$  for LY3074828. The secondary parameter for analysis will be the time to maximum observed drug concentration ( $t_{max}$ ) of LY3074828. Other noncompartmental parameters, such as half-life associated with the terminal rate constant ( $t_{1/2}$ ), apparent total body clearance of drug calculated after extra-vascular administration (CL/F), and apparent volume of distribution during the terminal phase after extra-vascular administration ( $V_z/F$ ), may be reported.

#### **10.3.2.2. Pharmacokinetic Statistical Inference**

The  $AUC(0-\infty)$ ,  $AUC(0-t_{last})$ , and  $C_{max}$  will be log-transformed and analyzed using a linear fixed-effects model. The model will include device and injection location as fixed effects. The dosing regimen differences between Test and Reference arms will be back-transformed to present the ratios of geometric LS means and the corresponding 90% CI.

The  $t_{max}$  of LY3074828 between Test and Reference arms will be analyzed using a Wilcoxon rank sum test. Estimates of the median difference, 90% CIs, and p-values from the Wilcoxon rank sum test will be calculated.

Additional PK analyses may be conducted if deemed appropriate.

### **10.3.3. Pharmacodynamic Analyses**

This section is not applicable for this study.

### **10.3.4. Pharmacokinetic/Pharmacodynamic Analyses**

This section is not applicable for this study.

### **10.3.5. Evaluation of Immunogenicity**

The frequency of formation of antibodies to LY3074828 will be determined.

Treatment-emergent ADAs are those that are induced or boosted by exposure to study drug, with a 4-fold or greater increase in titer compared to baseline if ADAs were detected at baseline, or a titer 2-fold greater than the minimum required dilution (1:10) if no ADAs were detected at baseline.

If a neutralization assay is performed, the frequency of neutralizing antibodies will be determined. The relationship between the presence (or absence) of antibodies and clinical parameters (AEs) will be assessed. Likewise, the relationship between the presence of antibodies and the PK parameters or concentrations of LY3074828 may be assessed if deemed appropriate.

#### ***10.3.6. Data Review During the Study***

Data may be accessed and analyzed while the trial is ongoing, but no changes to the study design are planned. An assessment committee will not be formed.

Available safety data will be reviewed at approximately Day 30 of the last cohort dosed in order to review emerging safety and tolerability data.

#### ***10.3.7. Interim Analyses***

Exploratory interim analysis is scheduled to occur upon completion of all VAS assessments for all subjects. The analysis will include determination of the mean/median VAS scores and standard deviation, and categorical grouping of VAS data. The VAS data from all 3 cohorts will be included in this interim analysis. The purpose of the interim analysis is to examine the data prior to distribution to other teams within Eli Lilly & Company. The analysis will be for internal purposes only and there is no intention for the analysis to change the conduct of the trial.

**Appendix 1. Abbreviations and Definitions**

---

Term	Definition
ADA	anti-drug antibody
AE	adverse event: Any untoward medical occurrence in a patient or clinical investigation subject administered a pharmaceutical product that does not necessarily have a causal relationship with this treatment. An AE can therefore be any unfavorable and unintended sign (including an abnormal laboratory finding), symptom, or disease temporally associated with the use of a medicinal (investigational) product, whether or not related to the medicinal (investigational) product.
AI	autoinjector
ALP	alkaline phosphatase
ALT	alanine aminotransferase
AUC	area under the concentration versus time curve
AUC(0-∞)	area under the concentration versus time curve from time zero to infinity
AUC(0-tlast)	area under the concentration versus time curve from time zero to time t, where t is the last sample with a measurable concentration
BMI	body mass index
CI	confidence interval
CL/F	apparent total body clearance of drug calculated after extra-vascular administration
Cmax	maximum observed drug concentration
complaint	A complaint is any written, electronic, or oral communication that alleges deficiencies related to the identity, quality, purity, durability, reliability, safety or effectiveness, or performance of a drug or drug delivery system.
compliance	Adherence to all the study-related requirements, good clinical practice (GCP) requirements, and the applicable regulatory requirements.
confirmation	A process used to confirm that laboratory test results meet the quality requirements defined by the laboratory generating the data and that Lilly is confident that results are accurate. Confirmation will either occur immediately after initial testing or will require that samples be held to be retested at some defined time point, depending on the steps required to obtain confirmed results.
CP	clinical pharmacologist
CRP	clinical research physician
CRU	clinical research unit
ECG	electrocardiogram
eCRF	electronic case report form

ED	early discontinuation
enroll	The act of assigning a subject to a treatment. Subjects who are enrolled in the study are those who have been assigned to a treatment.
enter	Subjects entered into a study are those who sign the informed consent form directly or through their legally acceptable representatives.
GCP	good clinical practice
GPS	Global Patient Safety
HIV	human immunodeficiency virus
IB	Investigator's Brochure
ICF	informed consent form
ICH	International Council for Harmonisation
IFU	Instructions for Use
IL-23	interleukin-23
informed consent	A process by which a subject voluntarily confirms his or her willingness to participate in a particular study, after having been informed of all aspects of the study that are relevant to the subject's decision to participate. Informed consent is documented by means of a written, signed and dated informed consent form.
interim analysis	An interim analysis is an analysis of clinical study data, separated into treatment groups, that is conducted before the final reporting database is created/locked.
investigational product (IP)	A pharmaceutical form of an active ingredient or placebo being tested or used as a reference in a clinical study, including products already on the market when used or assembled (formulated or packaged) in a way different from the authorized form, or marketed products used for an unauthorized indication, or marketed products used to gain further information about the authorized form.
investigator	A person responsible for the conduct of the clinical study at a study site. If a study is conducted by a team of individuals at a study site, the investigator is the responsible leader of the team and may be called the principal investigator.
IRB	institutional review board
ISR	injection-site reaction
IV	intravenous(ly)
LS	least squares
open-label	A study in which there are no restrictions on knowledge of treatment allocation, therefore the investigator and the study participant are aware of the drug therapy received during the study.

randomize	The process of assigning subjects/patients to an experimental group on a random basis.
PC	product complaint
PFS	pre-filled syringe
PK	pharmacokinetic(s)
SAE	serious adverse event
SC	subcutaneous(ly)
screen	The act of determining if an individual meets minimum requirements to become part of a pool of potential candidates for participation in a clinical study.
SUSARs	suspected unexpected serious adverse reactions
<math>t_{1/2}</math>	half-life associated with the terminal rate constant
TB	tuberculosis
TBL	total bilirubin
TE-ADA	treatment-emergent anti-drug antibody
TEAE	treatment-emergent adverse event: Any untoward medical occurrence that emerges during a defined treatment period, having been absent pretreatment, or worsens relative to the pretreatment state, and does not necessarily have to have a causal relationship with this treatment.
Th	T helper
<math>t_{max}</math>	time to maximum observed drug concentration
ULN	upper limit of normal
VAS	visual analog scale
<math>V_z/F</math>	apparent volume of distribution during the terminal phase after extra-vascular administration

---

## Appendix 2. Clinical Laboratory Tests

---

### Safety Laboratory Tests

Hematology a	Clinical Chemistry a
Hematocrit	Sodium
Hemoglobin	Potassium
Erythrocyte count (RBC)	Calcium
Mean cell volume	Phosphorus
Mean cell hemoglobin	Glucose (random)
Mean cell hemoglobin concentration	Blood urea nitrogen (BUN)
Leukocytes (WBC)	Uric acid
Cell morphology	Total cholesterol
Absolute counts of:	Total protein
Neutrophils	Albumin
Lymphocytes	Total bilirubin c
Monocytes	Alkaline phosphatase (ALP)
Eosinophils	Aspartate aminotransferase (AST)
Basophils	Alanine aminotransferase (ALT)
Platelets	Creatinine
	Creatine phosphokinase (CPK) d
Urinalysis a	Ethanol testing e
Specific gravity	Urine drug screen e
pH	QuantiFERON-TB Gold test a,f
Protein	
Glucose	
Ketones	Serologyf
Bilirubin	Hepatitis B surface antigen
Urobilinogen	Hepatitis C antibody
Blood	HIV antibodies
Nitrite	
Microscopic examination of sediment b	Serum Pregnancy test g,h
	Hormone Panel
	Follicle-stimulating hormone f,i

Abbreviations: HIV = human immunodeficiency virus; RBC = red blood cells; TB = tuberculosis; WBC = white blood cells.

a Results will be validated by the local laboratory at the time of initial testing.

b If clinically indicated, per investigator's discretion.

c If total bilirubin is elevated, direct bilirubin and indirect bilirubin may be measured.

d Not collected routinely as part of clinical chemistry panel. Only collected when specified in Schedule of Activities (Section 2).

e Urine drug screen and ethanol level (determined via breath, blood, or urine testing) will be performed locally at screening and on Day -1 during admission to the clinical research unit. May be repeated at the discretion of the investigator.

f Performed at screening only.

g For all females at screening and on Day -1, and only for women of childbearing potential at sampling time points thereafter.

h Refer to Section 2 for specific sampling timing.

i To confirm postmenopausal status.

---

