### 3.3. Benefit/Risk Assessment

Based on LY3074828 nonclinical and preliminary clinical data, there are no anticipated risks requiring monitoring beyond those for a typical humanized monoclonal antibody in human studies. As with other immunomodulatory therapies, LY3074828 may increase the risk of developing an infection or may exacerbate an existing serious infection. These may include opportunistic infections and reactivation of latent infections, such as tuberculosis (TB) and hepatitis B. Subjects will therefore be screened for hepatitis B/C, human immunodeficiency virus (HIV), and TB. Immunomodulatory therapies may increase the risk of malignancies; however, due to only single doses of LY3074828 being administered in this study, it is not considered necessary to monitor for such effects.

Based on available data from Studies AMAA and AMAD, TE-ADAs have been observed in 2 of the 11 healthy subjects that received SC doses of LY3074828; however, titers were  $\leq 1:160$ . In the 33 patients with psoriasis who received single IV doses of LY3074828, TE-ADAs were detected in 3 subjects (Study AMAA).

No clinically significant safety or tolerability concerns have been identified in patients or healthy subjects to date for LY3074828 up to the highest doses given (single 1200-mg IV doses and 2400-mg SC doses).

Healthy subjects are not expected to derive any benefit from participating in studies with administration of LY3074828.

As this study will use PFS and AIs, device-based risks will be evaluated. Possible device-based risks include local effects such as pain at the injection sites from either the needle or the solution entry into the SC tissue, swelling, erythema, bleeding, and bruising. These risks are mitigated by training of investigative site staff on proper injection techniques. Systemic effects may include sweating, feeling faint, or fever, as a sign of infection.

More information about the known and expected benefits, risks, SAEs, and reasonably anticipated AEs of LY3074828 are found in the IB.

More information about the known and expected benefits, risks, SAEs, and reasonably anticipated AEs of the AI is found in the device IB.

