[4] have clinical laboratory test results within normal reference range for the investigative site, or results with acceptable deviations that are judged to be not clinically significant by the investigator

[5] have venous access sufficient to allow for blood sampling as per the protocol

[6] are reliable and willing to make themselves available for the duration of the study and are willing to follow study procedures

[7] are able and willing to give signed informed consent

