## 6.2. Exclusion Criteria

Subjects will be excluded from study enrollment if they meet any of the following criteria at screening and/or enrollment:

[8] are investigative site personnel directly affiliated with this study and their immediate families. Immediate family is defined as a spouse, biological or legal guardian, child, or sibling

[9] are Lilly employees or employees of Covance

[10] are currently enrolled in a clinical study involving an investigational product (IP) or any other type of medical research judged not to be scientifically or medically compatible with this study

[11] have participated in a clinical trial involving an IP within 30 days or 5 half-lives (whichever is longer) prior to screening. If the clinical trial involved treatment with biologic agents (such as monoclonal antibodies, including marketed drugs), at least 3 months or 5 half-lives (whichever is longer) should have elapsed prior to Day 1

- [12] have previously completed or withdrawn from this study or any other study investigating LY3074828, and have previously received the IP
- [13] have known allergies to LY3074828, related compounds, or any components of the formulation, or history of significant atopy
- [14] have an abnormality in the 12-lead ECG that, in the opinion of the investigator, increases the risks associated with participating in the study
- [15] have an abnormal blood pressure as determined by the investigator
- [16] have a history or presence of cardiovascular, respiratory, hepatic, renal, gastrointestinal, endocrine, hematological, or neurological disorders capable of significantly altering the absorption, metabolism, or elimination of drugs; of constituting a risk when taking the IP; or of interfering with the interpretation of data
- [17] have known or ongoing psychiatric disorders deemed clinically significant by the investigator
- [18] regularly use known drugs of abuse and/or show positive findings on drug screening
- [19] show evidence of HIV infection and/or positive HIV antibodies
- [20] show evidence of hepatitis C and/or positive hepatitis C antibody
- [21] show evidence of hepatitis B and/or positive hepatitis B surface antigen
- [22] are women who are lactating

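### Low-severity improvement: Section 3.3 screens because latent hepatitis B may reactivate, but surface antigen, the only hepatitis B test before dosing, does not cover unrecognised antigen-negative infection

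*Protocol*

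**What the plan says.** Section 3.3 of the protocol describes the infection risk of immunomodulatory therapies, including this drug: "These may include opportunistic infections and reactivation of latent infections, such as tuberculosis (TB) and hepatitis B". The next sentence draws the consequence: "Subjects will therefore be screened for hepatitis B/C, human immunodeficiency virus (HIV), and TB".

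The Schedule of Activities refers serology to Appendix 2. There the only hepatitis B entry is "Hepatitis B surface antigen", and a footnote limits serology to the screening visit. Exclusion [21] removes subjects who "show evidence of hepatitis B and/or positive hepatitis B surface antigen".

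Two other criteria bear on liver status. Exclusion [16] covers subjects who "have a history or presence of cardiovascular, respiratory, hepatic, renal, gastrointestinal, endocrine, hematological, or neurological disorders", where the disorder could affect drug handling, risk or interpretation. Inclusion [4] asks that subjects "have clinical laboratory test results within normal reference range for the investigative site", or have deviations the investigator judges not clinically significant.

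After dosing, Section 9.4.5.1 requires repeat liver tests within 3 to 5 days once ALT, ALP or bilirubin passes a threshold. Appendix 4 offers an optional liver work-up that includes hepatitis B surface antigen and surface antibody.

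**The concern.** The stated reason for screening is latent infection. For tuberculosis, the other latent infection named, the protocol uses a test that it describes as covering active or latent disease. For hepatitis B it uses a marker of current infection. A subject who had hepatitis B without knowing it, who is now antigen-negative and whose laboratory results are acceptable, meets every listed criterion and would be dosed.

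What is at stake is subject protection. Section 3.3 says: "Healthy subjects are not expected to derive any benefit from participating in studies with administration of LY3074828". With no benefit on the other side of the balance, screening before exposure is the stated protection against this stated risk. Section 5.4 groups the compound with antibodies that have long half-lives, so exposure cannot be withdrawn quickly if a liver signal appears.

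**Working it through.** The plan has no figure of its own to reproduce on this point, so the main check compares sections. Arithmetic is needed only for the cost of the fix.

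**Step 1. The two latent infections named in Section 3.3**

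| | Tuberculosis | Hepatitis B |
|---|---|---|
| Named as able to reactivate | Yes | Yes |
| Test before dosing | QuantiFERON-TB Gold, for active or latent infection (9.4.4.1) | Surface antigen (Appendix 2) |
| Exclusion criterion | [28], active or latent | [21], evidence of hepatitis B or positive antigen |

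Hepatitis B markers before dosing: 1. In the optional post-dose work-up of Appendix 4: 2. Core antibody: 0 in both lists.

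**Step 2. Who is stopped before dosing**

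| Subject | Stopped by |
|---|---|
| Surface-antigen-positive, including carriers | [21], antigen limb |
| Known past hepatitis B or relevant liver disorder | [21], evidence limb; [16] |
| Unrecognised infection with clinically significant abnormal liver tests | [4] |
| Unrecognised, antigen-negative, acceptable laboratory results | No listed test or criterion identifies it |

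The last row is the whole gap. That an antigen test cannot identify an antigen-negative subject, and that core antibody marks past exposure, is general laboratory knowledge; the documents do not state it.

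**Step 3. Does the single dose already answer the point?** For malignancy, Section 3.3 says: "due to only single doses of LY3074828 being administered in this study, it is not considered necessary to monitor for such effects". It makes no such waiver for infection, where screening is kept.

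**Step 4. Cost in screen failures.** The documents give no prevalence of core antibody. Let p be an assumed prevalence among otherwise eligible volunteers. The expected number of extra screen failures to randomize 66 subjects is 66 × p / (1 − p):

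- p = 0.5%: 66 × 0.005 / 0.995 = 0.33
- p = 1%: 66 × 0.01 / 0.99 = 0.67
- p = 2%: 66 × 0.02 / 0.98 = 1.35
- p = 5%: 66 × 0.05 / 0.95 = 3.47

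**Step 5. Chance of enrolling at least one such subject without the test.** This is 1 − (1 − p)^66: 28% at p = 0.5% and 97% at p = 5%. It rests on the same assumed range. It is a chance of enrolment, not of reactivation.

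**Step 6. Blood volume.** The Appendix 5 total reproduces: 22.5 + 62.5 + 34 + 50 + 14 + 10 = 193 mL, rounded up there to 200 mL. The documents give no tube allocation. If an extra tube of 3.5 to 5 mL were needed (assumed), the total would be 196.5 to 198 mL, a rise of 3.5/193 = 1.8% to 5/193 = 2.6%.

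**The case against.** The strongest reply is that nothing is broken. Section 3.3 promises hepatitis B screening, and Appendix 2 with exclusion [21] delivers it. Surface antigen finds carriers, who can reactivate. Criterion [28] mentions latent TB explicitly; [21] makes no matching promise, and Section 3.3 does not say that each infection will be screened to the same depth. All of this stands. A reader might infer from Section 3.3 that the plan commits to detecting latent hepatitis B and then fails to do so. The text does not go that far: the screen is partial, not contradictory.

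The second reply is that the risk is small. Exclusions [23], [30], [31] and [32] remove most recent medication, recent oral steroids, immunocompromised subjects and recent biologics, so added immunosuppression is unlikely. Chemistry with ALT, AST, ALP and bilirubin is repeated during the 12-week follow-up and feeds the Section 9.4.5.1 rules. Section 3.2 reports about 819 participants in studies of the drug (placebo or active) and no deaths, serious adverse events or discontinuations due to adverse events in Phase 1. Section 3.3 reports no clinically significant safety concern up to single doses of 1200 mg IV and 2400 mg SC. This also stands, and it sets the severity. It does not remove the point. Those exclusions do not detect the infection, the chemistry rules act only after exposure, and the documents do not give the hepatitis B status of earlier participants.

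A third reply is that excluding every core-antibody-positive volunteer is blunt, since many may have resolved infection and a reflex HBV DNA test could sort them. True, but in a small healthy-volunteer study simple exclusion is adequate and easier to run.

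**Conclusion.** The point holds as a low-severity safety improvement. The screening panel leaves one identifiable group uncovered: subjects with unrecognised, surface-antigen-negative past or occult hepatitis B and acceptable laboratory results. The sample size, precision, endpoints and analyses are unaffected.

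No risk figure can be given. A reader might take the 28% to 97% above as a measure of harm, or infer that subjects face a material risk of reactivation. The documents support neither. They give no prevalence and no reactivation rate, and Section 3.3 says only that the drug may increase infection risk. After one 250-mg dose, with the exclusions and follow-up described, the absolute risk is probably low.

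The case for acting rests on three things: the protocol itself names the risk, the subjects expect no benefit, and the remedy costs very little. The conclusion assumes only the general test knowledge noted in the working; the prevalence and tube volumes are assumptions that affect the cost of the fix alone.

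**What to change.** Add total hepatitis B core antibody to the screening serology in Appendix 2, taken at the existing screening draw. Extend exclusion [21] with the words *and/or positive hepatitis B core antibody*, so that a positive result has a defined consequence.

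The cost is one more assay per screened subject (the documents give no price), with no extra visit or venipuncture. Expect at most a few extra screen failures, about 0.3 to 3.5 under the assumed prevalence range; Section 6.4 does not allow these people to be re-screened. If another tube is needed, Appendix 5 should be updated; the total stays under the 200 mL already stated.
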